1.2 SCHEMA

Prior to Enrollment

Total N=60 Obtain informed consent. Screen potential participants by inclusion and exclusion criteria. Parents complete baseline questionnaire and provide height and weight measurements of the children. Children complete the cognitive assessments. Participants allocated into intervention (arm 1, N=30) or placebo (arm 2), N=30).

[figure not shown]

Intervention Information

Intervention

Study Period (6 months). Participants will take 1 scoop of the powder every morning, mixed with water, milk, or a smoothie.

Participants will complete questionnaires at Months 1, 2, 3, 4, 5, 6 and provide height and weight measurements of the children at Month 2, Month 4, and Month 6. Children will repeat cognitive assessments at Month 6 (endline).

1.3 SCHEDULE OF ACTIVITIES (SOA)

Procedures	Screening	Intervention	Conclusion
Informed Consent	х		
Demographics	х		
Inclusion/ Exclusion	х		
Administer Study Intervention		х	
Questionnaires	х	Х	х
Height & Weight Measurements	х	х	х
Cognitive Battery Testing	х		х
Adverse event Review and Evaluation	х	Х	Х

2 INTRODUCTION

2.1 STUDY RATIONALE

Protein is fundamental to growth and the repair of body tissues; hence, its adequacy in children's diets is critical for optimal physical development. Studies have highlighted the role of dietary protein in increasing height and weight in children, suggesting a direct correlation between protein intake and growth metrics¹⁻³. Similarly, essential vitamins such as Vitamin A, C, D, E, and B-complex and minerals like Calcium, Iron, and Zinc have well-documented contributions to other aspects of physical development, bone health, immune function, and cognitive development^{4,5}. For instance, Vitamin D's role in bone mineralization is well-documented⁶, while Iron and Zinc have been associated with cognitive function and immune defense⁷ Furthermore, emerging research on the gut-brain axis underscores the significance of digestive health in cognitive and immune system functions, advocating for the inclusion of probiotics and prebiotic fibers in dietary regimens for children⁸.

In the USA, many people are at risk of vitamin, mineral, and/or other micronutrient deficiencies⁹⁻¹¹. Children and adults are consuming more low-nutrient foods with added sugar and excess fats as compared to healthy, high-quality calories and micronutrients. The risk of this is further exacerbated by socioeconomic and family income to poverty ratio¹⁰. However, research has suggested that dietary supplements can be helpful in meeting nutrient requirements for some micronutrients.

With this in mind, the test product has been developed and contains a proprietary blend of vitamins, minerals, and probiotics designed to enhance children's and teenager's health outcomes through the aforementioned mechanisms. This study will assess the effects of the test product on a range of health outcomes in children over the course of 6 months.

2.2 RISK/BENEFIT ASSESSMENT

Immediate risks:

There are no predicted risks associated with this product. However, some people may experience adverse reactions when trying a new product. NuBest Tall Protein contains milk-based ingredients, so it is not suggested for those with a dairy allergy. It does not contain soy, grain, wheat, GMO, or gluten.

As dairy can interact with a number of medications, all medications should be separated by a minimum of 4 hours from taking the test product.

Long-term risks:

There are no predicted long-term risks related to using this product. Any short-term risk should dissipate after discontinuing the test product.

Immediate benefits:

Participants may experience positive changes in overall health. Also, participants might experience increased energy levels, immune function, and overall well-being.

Long-term benefits:

Participants may experience an increase in height, maintenance of a healthy weight, and enhanced quality of life due to an increase in overall health.

3 OBJECTIVES AND ENDPOINTS

OBJECTIVES	ENDPOINTS	TIMEPOINTS	ASSESSED BY	JUSTIFICATION FOR ENDPOINTS
Primary				
To examine the effect of the NuBest Tall Growth Protein Powder cognitive function.	Improvement in score on assessments: • Double Trouble • Feature Match • Grammatical Reasoning • Digit Span • Token Search	Baseline and Month 6	Cognitive Battery Testing	The combination of these cognitive assessments will provide objective data on the efficacy of the product in improving specific domains of cognitive function.
Secondary				
	Increase in height			

	Maintenance of a healthy weight	Baseline, Month 2, Month 4, Month 6 (height & weight measurements)	Height measured using an Ultrasonic Height	
To investigate the impact of the NuBest Tall Growth Protein Powder on a range of health parameters, including height, weight, energy levels, immune function, and digestion.	Increase energy levels		Measuring Stadiometer	The combination of objective measurements and questionnaires will provide both independent and participant perception data on secondary health parameters.
	Improved signs of digestive health		Weight measured using a FitBit Smart Scale.	
	Increased immune	Baseline, Month 1, Month 2, Month 3, Month 4, Month 5, Month 6.		
	function (assessed via the number of times the child has been ill in the past 6 months)		Study-specific questionnaires	

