5.2 EXCLUSION CRITERIA

An individual who meets the following criteria will be excluded from participation in this study:

- 1. Any child with a history of endocrine disorder, heart disease, lung disease, kidney disease, digestive disease or skeletal dysplasia.
- 2. Any pre-existing chronic conditions that would prevent participants from adhering to the protocol, including oncological and psychiatric disorders.
- 3. Is undergoing or planning to undergo significant medical procedures in the next six months.
- 4. A history of severe allergic reactions, including but not limited to any of the product's ingredients.
- 5. Any child with a dairy allergy or lactose intolerance.
- 6. Has undergone any surgeries or invasive treatments in the last six months.
- 7. Has had any major illness in the last three months.
- 8. Having any planned invasive medical procedures during the study period
- 9. Currently participating in any other clinical study.
- 10. Unwilling to follow the study protocol.
- 11. Any child diagnosed with attention-deficit disorder (ADD) or attention-deficit hyperactivity disorder (ADHD).
- 12. Any child currently taking, or have they taken in the last 3 months, any prescription medication targeting ADD or ADHD (such as Adderall, Concerta, Focalin, Evekeo, or Ritalin).
- 13. Any child that is a 'fussy' eater or who the parent suspects may not tolerate consuming the test product daily for six months.

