6 STUDY INTERVENTION

6.1 STUDY INTERVENTION

- Potential participants (parents + child) who meet the initial inclusion and exclusion criteria can participate in this trial
- If participants meet the inclusion and exclusion criteria after the parents have signed the informed consent, participants will begin the trial.
- The parents will complete the Baseline questionnaire and provide the Baseline height and weight measurements of the children. The children will complete the Baseline cognitive assessments.
- After the baseline data collection, participants will be randomly allocated into the intervention or placebo study group. The participants and Citruslabs will not be informed who is in the intervention or the placebo group.
- The children will take 1 one scoop of the powder mixed with 6-8 oz of water, milk, or smoothies every morning.
- Parents will complete questionnaires at the end of Month 1, Month 2, Month 3, Month 4, Month 5, and Month 6.
- Parents will provide height and weight measurements of the children at Month 2, Month 4 and Month 6.
- The children will repeat the cognitive assessments at the end of Month 6.
- Completion of the Month 6 measurements marks the end of the study.

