6.4 PARTICIPANT DISCONTINUATION/WITHDRAWAL FROM THE STUDY

Participants are free to withdraw from participation in the study at any time upon request.

An investigator may discontinue or withdraw a participant from the study for the following reasons:

- Pregnancy
- Significant study intervention non-compliance
- If any clinical adverse event (AE), laboratory abnormality, or other medical condition or situation occurs such that continued participation in the study would not be in the best interest of the participant
- Disease progression which requires discontinuation of the study intervention
- If the participant meets an exclusion criterion (either newly developed or not previously recognized) that precludes further study participation
- Participant should be withdrawn from the study if they start on a new drug or receive antibiotics

The reason for participant discontinuation or withdrawal from the study will be recorded on a Case Report Form (CRF). Participants who sign the informed consent form but do not receive the study intervention may be replaced. Participants who sign the informed consent form, receive the study intervention, and subsequently withdraw, or are withdrawn or discontinued from the study, will not be replaced.

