7 STATISTICAL CONSIDERATIONS

Following data collection and the completion of the trial, the data will be analyzed by Citruslabs to determine the effect of the intervention versus the placebo. Between-arm and participant repeated measures between time point statistical tests will be used to examine differences in health outcomes during the study and compared to the placebo. Percentages of people who experienced improvements will also be examined. The analysis will adopt an intent-to-treat (ITT) approach, reflecting the primary objective of assessing the effectiveness of the test product as it would be used in the general population, inclusive of all randomized participants, irrespective of adherence or protocol deviations.

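### The immune endpoint asks for six months of illness at every monthly questionnaire, so the Month 1 to 5 counts are 83% to 17% pre-randomisation time

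*Combined protocol and SAP*

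**What the plan says.** The objectives table in section 3 lists, among the secondary endpoints, increased immune "function (assessed via the number of times the child has been ill in the past 6 months", collected by study-specific questionnaire. The timepoints printed for it are "Baseline, Month 1, Month 2, Month 3, Month 4, Month 5, Month 6".

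Section 6.1 fixes the time origin: "After the baseline data collection, participants will be randomly allocated into the intervention or placebo study group". The whole Baseline recall window therefore lies before randomisation. The same section confirms the follow-up schedule: "Parents will complete questionnaires at the end of Month 1, Month 2, Month 3, Month 4, Month 5, and Month 6". Treatment lasts six months.

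On analysis, section 7 says only that "Between-arm and participant repeated measures between time point statistical tests will be used to examine differences in health outcomes during the study", with a comparison against placebo, and that "Percentages of people who experienced improvements will also be examined". It names no visit, total or model for the immune endpoint. No section shortens the recall period after Baseline or restricts the illness item to Baseline and Month 6.

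**The concern.** A six-month look-back asked one month after randomisation mostly describes the child's health before any product was taken. Randomisation balances that earlier illness between arms in expectation, so it cannot create a false benefit, but it pulls the comparison towards no difference. The windows also overlap heavily. An illness in the first on-study month falls inside all six follow-up windows, so a repeated-measures test would be analysing largely the same events several times.

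The percentage-improved analysis is affected as well. At Month 1, change from Baseline turns out to compare one month on study with a single month half a year earlier (shown below), which says very little about treatment.

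If Months 1 to 5 enter the analysis without allowance for the growing on-treatment share, a real reduction in illness will be understated. If only Month 6 is used, the result rests on one six-month parental recall, although parents are already contacted every month.

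**Working it through.** The plan states no figure for this point, so there is none to reproduce.

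**Inputs from the documents.** Recall window of 6 months and questionnaires at Months 1 to 6 (section 3); randomisation after Baseline (section 6.1); 6 months of treatment (synopsis); 30 children per arm (section 5.4).

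**Step 1: pre-randomisation share.** At Month k the window reaches back 6 months, of which 6 − k precede randomisation. The share is (6 − k)/6.

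**Step 2: apparent rate ratio.** Assume a constant illness rate and a true ratio of 0.70 (illustrative, not in the documents). With an immediate effect, the apparent ratio is (1 − k/6) + 0.70 × k/6. If the effect starts only after 2 months, the affected months number max(0, k − 2), and the ratio is (6 − affected + 0.70 × affected)/6.

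| Month | Pre-randomisation share | Apparent ratio, immediate effect | Apparent ratio, onset after 2 months |
|---|---|---|---|
| 1 | 83.3% | 0.95 | 1.00 |
| 2 | 66.7% | 0.90 | 1.00 |
| 3 | 50.0% | 0.85 | 0.95 |
| 4 | 33.3% | 0.80 | 0.90 |
| 5 | 16.7% | 0.75 | 0.85 |
| 6 | 0% | 0.70 | 0.80 |
| Equal-weight mean | 41.7% | 0.825 | 0.917 |

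With an immediate effect, the equal-weight mean keeps (1 − 0.825)/(1 − 0.70) = 0.583 of the true effect, a dilution of 41.7%. That figure applies only if all six visits are weighted equally.

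**Step 3: overlap.** Windows one month apart share 5 of 6 months, or 83.3%.

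**Step 4: change from Baseline.** Number the six baseline months from oldest (1) to most recent (6). The Month k window holds baseline months k + 1 to 6 plus on-study months 1 to k. Subtracting the Baseline window leaves on-study months 1 to k minus baseline months 1 to k. At k = 1 this is one on-study month minus the single oldest baseline month.

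**Step 5: start of dosing.** The 0% at Month 6 assumes that dosing starts at randomisation or that months are counted from first dose. The documents give no lag. If months are counted from randomisation, an assumed lag of 0.25 or 0.5 month leaves 4.2% (0.25/6) or 8.3% (0.5/6) of the Month 6 window before first dose, and the earlier windows are slightly worse.

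**Step 6: power.** The assumptions, none of them in the documents, are 2 to 4 illnesses per child per six months, overdispersion 0.3 to 0.6, perfect recall, no dropout and a true ratio of 0.70. There were 800 simulated trials per setting, with gamma-Poisson monthly illnesses, 30 per arm, Poisson regression with robust standard errors adjusted for log(baseline + 0.5), and two-sided 0.05.

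| Analysis | Power |
|---|---|
| Month 1 | 10–12% |
| Month 3 | 19–29% |
| Average of six visits | 29–45% |
| Month 6, or total on-study count | 35–55% |

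Averaging costs about 6 to 10 points (35 − 29 and 55 − 45). Under no effect, this test rejected in 5 to 8% of simulated trials, so these powers are if anything slightly generous.

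**The case against.** The strongest reply concerns the reading of section 3. The table was broken when its text was extracted, the list of months looks like a cell shared by all questionnaire endpoints, and the questionnaire itself is not available. The recall length equals the treatment length, so a matched Baseline and Month 6 pair could have been intended. That is possible, but no section says so. The table prints Months 1 to 5, and section 7 plans tests between timepoints. Either way section 3 needs a correction, so the uncertainty changes which edit is made, not whether one is needed.

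Second, the harm depends on an analysis the plan does not specify. A Month 6 between-arm contrast has no dilution, nobody has proposed averaging six visits, and the dilution runs towards the null. All of this stands. But the plan does not choose Month 6, and the analyses it does describe invite use of the earlier visits.

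Third, under perfect recall the proposed on-study total has the same power as Month 6. This also stands: no power gain over naming Month 6 has been shown. The case for monthly counts is that they avoid a six-month recall, and the documents give no figure for how much accuracy that buys.

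Season, and the exclusion of a child who "Has had any major illness in the last three months", can shift within-arm change from Baseline, but they do not bias the randomised comparison.

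**Conclusion.** The concern holds for the endpoint as written. The pre-randomisation shares, the overlap and the change-from-Baseline identity follow exactly from section 3 and section 6.1, taking Baseline and randomisation as simultaneous. The ratios of 0.95 down to 0.70 also need a constant illness rate and an immediate effect; a delayed effect makes the understatement worse. The power figures rest on assumed illness rates and should be read only as a guide.

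The main damage is an understated effect size wherever Months 1 to 5 are used; the power lost by averaging is secondary. This is a secondary endpoint, so the plan should be changed, but the primary conclusion is not at risk. Confidence is moderate because the questionnaire wording has not been seen.

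**What to change.** First check the questionnaire. If it already uses a shorter recall after Baseline, correct the definition in section 3 and state which visit or total is analysed.

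If it does not:

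- Keep the six-month question at Baseline, as a covariate only.
- At Months 1 to 6, ask for new illness episodes since the last questionnaire. The six windows then add up to the treatment period, with no overlap and no pre-randomisation time.
- Compare total on-study episodes per child between arms with a count model, for example negative binomial with log observed time as offset, adjusted for baseline count, age and sex.
- Base the immune conclusion on that comparison, not on within-arm change or percentage improved from Baseline.

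If the item cannot be reworded, naming the Month 6 between-arm contrast removes the dilution but keeps the long recall.

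The cost is one reworded item and a short analysis paragraph, with no extra visits. The Baseline and follow-up items will no longer be identical, so within-arm change is not shown. Section 6.4 also says "Participant should be withdrawn from the study if they start on a new drug or receive antibiotics", so illness itself can end follow-up, and the time offset does not fully remove that. An optional sensitivity analysis would impute unobserved months in both arms at 1, 1.5 and 2 times the placebo-arm rate.

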Description of Study Intervention:	 After eligibility is established, participants will complete a Baseline questionnaire, the Baseline cognitive assessment, and provide the Baseline height and weight measurements. Participants will be randomly allocated to either the intervention or placebo group. The participants and Citruslabs will not be informed who is in the test or the placebo group. Participants will begin taking their respective product for 6 months. The children will drink one scoop of the powder mixed with 6-8 oz of water, milk, or smoothies. Parents will complete questionnaires at the end of Month 1, Month 2, Month 3, Month 4, Month 5, and Month 6, and will provide further height and weight measurements at Month 2, Month 4, and Month 6. The children will repeat the cognitive assessments at Month 6 (endline). 		
Study Duration:	6 months		
Participant Duration:	6 months		
Product Instructions:	 The test products must be consumed in the morning. Combine one scoop of the powder with 6-8 oz of water, milk, or smoothies. Do not use NuBest Protein Powder for baking or cooking recipes. 		
Stadiometer Instructions:	 Step 1: Upon powering on the device, securely affix it to the wall, ensure that the height measuring instrument remains perpendicular to the ground and parallel to the wall at a 90-degree angle. Step 2: Once you've adjusted the height accordingly, press the measurement key only in the absence of any obstacles. Choose a flat ground without steps, and try to avoid testing on carpets or uneven areas with plush carpets or rugs. Ensure the device is perpendicular to the ground. 		
Compensation	\$150 Visa gift cardFitBit Smart Scale		

Ultrasonic Height Measuring Stadiometer

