5.4 JUSTIFICATION OF SAMPLE SIZE

60 participants, 30 each in the intervention and placebo arms, is sufficient to establish differences between the two study conditions. This will allow for meaningful between-group comparisons to adequately assess the efficacy of the test product versus placebo control.

[figure not shown]

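### Baseline and Month 6 illness counts cover opposite halves of the year, so within-arm change can be confounded with season; efficacy on illness should rest on the between-arm comparison

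*Combined protocol and SAP*

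**What the plan says.** The protocol's Section 3 (Objectives and Endpoints, Secondary) measures increased immune "function (assessed via the number of times the child has been ill in the past 6 months"). The questionnaire time points in the same table are "Baseline, Month 1, Month 2, Month 3, Month 4, Month 5, Month 6".

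Section 6.1 puts the first questionnaire before treatment: "After the baseline data collection, participants will be randomly allocated into the intervention or placebo study group". The Synopsis fixes the treatment period: "Participants will begin taking their respective product for 6 months".

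Section 7 sets out the analysis in general terms: "Between-arm and participant repeated measures between time point statistical tests will be used to examine differences in health outcomes during the study". The sentence goes on to add a comparison with placebo, and the sentence before it gives the aim as the effect of intervention versus placebo. Section 7 then adds: "Percentages of people who experienced improvements will also be examined".

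The protocol gives no enrolment dates or enrolment period, no calendar-time or season covariate, and no definition of improvement. It does not say whether the percentages are read within an arm or compared between arms, or which test decides whether there is an effect.

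**The concern.** The look-back and the treatment period are both six months long. The Baseline count therefore describes the half-year before product, and the Month 6 count describes the other half of the calendar. If childhood illness varies with season, a child who starts in spring moves from a winter window to a summer window, and a child who starts in autumn does the reverse. A fall or rise in the count within one arm can then come from the calendar alone.

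Section 7 applies time-point tests and percentages improved to the health outcomes, and illness is one of them. If a within-arm result were read as evidence, an inert product could appear to reduce illness, or a useful one could appear to do nothing. Section 4.3 links the choice of dosage to establishing marketing claims, so how such a figure would be read matters.

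**Working it through.** **Inputs from the protocol.** Look-back 6 months (Section 3). Baseline before randomization (Section 6.1). Treatment 6 months (Synopsis). 30 children per arm (Section 5.4: "60 participants, 30 each in the intervention and placebo arms, is sufficient to establish differences between the two study conditions"). That sample size cannot be reproduced, because no significance level, power, effect size, variability, illness rate or dropout is given. No figure at all is stated for the illness endpoint.

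**Step 1: the windows.** A look-back at month m covers m − 6 to m.
- Baseline (m = 0): months −6 to 0.
- Month 6 (m = 6): months 0 to +6.

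They do not overlap, and 6 + 6 = 12 months. For every start date they are complementary halves of the year. This step needs no assumption.

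**Step 2: the seasonal shift in the mean.** Assume a rate that follows a yearly cosine with relative amplitude A, a mean of λ illnesses per six months, and Baseline d months after the peak. With an inert product:
- expected Baseline count = λ[1 + A(2/π)sin(πd/6)]
- expected Month 6 count = λ[1 − A(2/π)sin(πd/6)]

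With λ = 2, A = 0.5, d = 3: 2(1 + 0.5 × 0.637) = 2.64 and 2(1 − 0.5 × 0.637) = 1.36. With d = 0 the sine is zero and both are 2.00.

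**Step 3: what the tests then do.** Simulation with no product effect, 30 per arm, 10,000 runs per scenario, Poisson counts with gamma frailty (mean 1, shape 2), paired t-test within arm, t-test on change between arms, two-sided 0.05. λ, A, the tests and the timing are assumptions. Results for λ = 2, A = 0.5:

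| Baseline timing | Expected count, Baseline → Month 6 | Within-arm significant fall | Within-arm significant, either way | Improved, active / placebo | Between-arm significant |
|---|---|---|---|---|---|
| At peak | 2.00 → 2.00 | 2.5% | 4.9% | 36.6% / 36.4% | 4.8% |
| 1.5 months after peak | 2.45 → 1.55 | 64.8% | 64.8% | 53.0% / 52.9% | 5.1% |
| 3 months after peak | 2.64 → 1.36 | 90.9% | 90.9% | 59.5% / 59.4% | 4.8% |
| 3 months before peak | 1.36 → 2.64 | 0.0% | 90.8% | 16.7% / 16.7% | 4.8% |
| Spread over 12 months | 2.00 → 2.00 | 2.5% | 4.9% | 37.2% / 37.4% | 4.9% |

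Over λ = 1 to 3 and A = 0.3 to 0.7, with every Baseline three months after the peak, the within-arm test rejects in 28% to about 100% of trials. The between-arm rate stays between 4.4% and 5.5% throughout.

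**Step 4: a simpler model.** Independent Poisson counts, 20,000 trials, all children enrolled so that winter falls before Baseline. Assumed winter/summer means of 3/1.5, 3/2 and 2/1.5 give a significant within-arm fall in 97%, 66% and 29% of trials; 68%, 59% and 49% of children have fewer illnesses. With the seasons reversed, 17%, 25% and 29% do.

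**Step 5: comparing two within-arm p-values.** Showing each arm's own test side by side does not repair this. With an inert product the arms are independent, so a significant fall on active but not on placebo has probability p(1 − p): 0.665 × 0.335 = 0.22 for 3/2 and 0.286 × 0.714 = 0.20 for 2/1.5. With no seasonal shift it is 0.025 × 0.975 = 0.024.

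**Step 6: with a real effect.** Assume a 30% reduction, λ = 2, A = 0.5. With Baseline at the peak, the active arm's test rejects in 39.0% of trials against 4.9% on placebo, and 47.2% against 36.5% improve. With Baseline three months before the peak, the active arm's expected count rises from 1.36 to 1.85 and a significant fall appears in 0.1% of trials, so the calendar hides the effect.

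**The case against.** A reader might infer that the within-arm figures measure season and not the product, or that the confounding is complete. The documents do not support that. Opposite halves of the year need not carry different illness burdens: the shift is nil if Baseline falls at the peak or trough, and the mean shift averages out if enrolment runs for a year. Step 6 shows that the within-arm figures carry product effect as well as season. This part of the objection stands. The 97% and 91% figures belong to unfavourable timing and assumed rates.

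A reader might also infer that the plan ignores season. It has a concurrent randomized placebo arm, and Section 7 plans a comparison with it. Season acts on both arms alike, so that comparison is not biased. This stands too. It does not remove the point, because Section 7 plans the within-participant tests alongside the comparison and does not say which one decides.

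Nor does it follow that a percentage improved is invalid. Section 7 leaves open whether it is compared between arms; if it is, season cancels. The fault lies only in reading it within one arm, where about 37% of children improve with no product effect and no net seasonal shift.

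Finally, Section 4.3 mentions marketing claims to justify the dosage. It does not say that a claim will rest on within-arm illness change, so a false claim is a risk and not a stated intention. Small-block allocation is not needed either: randomization already balances calendar time on average.

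**Conclusion.** The point holds in a limited form. It is certain from the documents that the Baseline and Month 6 windows are opposite half-years, and that the planned within-participant tests and percentages improved have no exemption for illness and no seasonal adjustment. The within-arm change, and a percentage improved read within one arm, can therefore be confounded with season.

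The size is conditional. Under the assumed rates with an inert product, false significant falls range from about the nominal 2.5% to more than 90%, and under the opposite timing the error is in the unfavourable direction. Enrolment timing and seasonal amplitude decide where the trial lands, and the protocol gives neither. The between-arm comparison keeps its error rate in every scenario examined. This is one secondary endpoint; the change is worth making because it is cheap and removes a test that could mislead.

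**What to change.** In Sections 3 and 7, state for the illness endpoint that:

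- efficacy rests only on the between-arm difference in the Month 6 count, which covers the six months on product, with the Baseline count as a covariate;
- within-arm change is descriptive and is not evidence of effect;
- any percentage improved is defined, shown for both arms and compared between arms.

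Month 6 is the right visit because a six-month look-back at month m still contains (6 − m)/6 pre-treatment time: 83%, 67%, 50%, 33% and 17% at Months 1 to 5, and none at Month 6.

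The cost is a few sentences. No visit, procedure or sample size changes, and the Baseline count is already collected. The sponsor gives up a stand-alone before-after illness claim. It should also know that the valid comparison may have little power: under the assumed 30% reduction with λ = 2 and A = 0.5, the between-arm test of change was significant in 10% to 32% of trials, depending on timing. The power of the covariate-adjusted analysis was not computed.
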